6 OBJECTIVES

6.1 EFFICACY OBJECTIVES

6.1.1 Primary

The primary objective of this extension study is to assess the maintenance of efficacy of linzagolix administered orally once daily for up to an additional 6 months (for up to 12 months of treatment in total) in women who have already completed 6 months of linzagolix treatment at a dose of 75 mg alone or 200 mg in combination with ABT (E2 1 mg / NETA 0.5 mg) in the management of moderate to severe EAP in women with surgically confirmed endometriosis. The two co-primary efficacy endpoints will be clinically meaningful reduction over the last 28 days of randomized treatment up to the Month 12 visit, along with a stable or decreased use of analgesics for EAP for 1) dysmenorrhea (DYS) and for 2) non menstrual pelvic pain (NMPP).

6.1.2 Secondary

Secondary objectives include evaluation of efficacy over the last 28 days of randomized treatment up to the Month 12 visit based on the following parameters: evaluation of pain associated with sexual intercourse (dyspareunia) and defecation (dyschezia), difficulty of doing daily activities, analgesic use, assessment of subject perception of severity, change in uterine bleeding, Quality of Life (QoL) questionnaires, pharmacoeconomic burden of endometriosis by assessing changes in patient productivity, assessment of endometriosis-related number of non-study health visits, number of days in hospital and type of medical procedures performed during the Treatment Period.

6.2 SAFETY OBJECTIVES

Safety and tolerability objectives include assessment of BMD, endometrial health, cardiac safety including QT interval prolongation, standard laboratory safety parameters, gynecological assessments and AE frequency including specific hypoestrogenic AEs.

6.3 EXPLORATORY OBJECTIVES

Exploratory objectives include assessment of bone turnover markers and collection of PK and PD related data of linzagolix for a separate modelling exercise.

7 ENDPOINTS

7.1 EFFICACY ENDPOINTS

7.1.1 Primary

The two co-primary, composite efficacy endpoints are clinically meaningful reduction from baseline to the last 28 days preceding the Month 12 visit (the 4-week period preceding Month 12 visit) along with a stable or decreased use of analgesics for EAP, in the mean daily assessment of 1) DYS and of 2) NMPP measured on a Verbal Rating Scale (VRS) using an electronic diary (eDiary).

7.1.2 Secondary

The secondary endpoints include:

- Change from baseline to Month 12 in DYS (VRS)
- Change from baseline to Month 12 in NMPP (VRS)
- Change from baseline to Month 12 in dyschezia (Numeric Rating Scale - NRS)
- Change from baseline to Month 12 in overall pelvic pain (NRS)
- Change from baseline to Month 12 in the interference of pain with the ability to perform daily activities, measured using the pain dimension of the Endometriosis Health Profile-30 (EHP-30)
- Change from baseline to Month 12 in dyspareunia (VRS)
- No analgesics use for EAP during the preceding 4-week period at each scheduled assessment
- No opiate use for EAP during the preceding 4-week period at each scheduled assessment
- Responder rate at scheduled visit other than Month 12 visit, for DYS and NMPP (VRS)
- Change from baseline to each scheduled assessment in the mean pelvic pain scores for DYS, NMPP and overall pelvic pain, during the previous 4-week period assessed on the NRS and VRS
- Change from baseline to each scheduled assessment in the number of days with moderate to severe pelvic pain during the previous 4-week period assessed on the VRS

- Change from baseline to each scheduled assessment in the mean worst pelvic pain score defined as the mean of the 5 highest daily pain scores reported during the previous 4-week period assessed on the NRS
- Change from baseline to each scheduled assessment in the mean of daily dyspareunia scores reported during the previous 4-week period on the dyspareunia VRS
- Change from baseline to each scheduled assessment in the mean of daily dyschezia scores reported during the previous 4-week period assessed on the dyschezia NRS
- Change from baseline to each scheduled assessment in non-opioid, opioid and combined analgesic use for EAP during the previous 4-week period based on pill count in the eDiary
- Change from baseline to each scheduled assessment in opioid analgesic use for EAP as reported in the eDiary during the previous 4-week period based on morphine milligram equivalent (MME)
- Change from baseline to each scheduled assessment in the number of days of analgesic use (including any class) for EAP during the previous 4-week period as assessed in the eDiary
- Change from baseline to each scheduled assessment in the number of days of opioid analgesic use for EAP during the previous 4-week period as assessed in the eDiary
- Change from baseline to each scheduled assessment in the number of pelvic pain-free days (assessed on the VRS) during the previous 4-week period
- Change from baseline to each scheduled assessment in ability to perform daily activities during the previous 4-week period, as assessed in the eDiary (daily function NRS)
- Change from baseline to each scheduled assessment in the number of days with no difficulty in doing daily activities due to EAP during the previous 4-week period as assessed in the eDiary (daily function NRS)
- Change from baseline to each scheduled assessment in the number of days when dyspareunia was a problem during the previous 4-week period (including days when sexual intercourse was avoided because of anticipation of pain) as assessed on the dyspareunia VRS
- Change from baseline to each scheduled assessment in the number of days when sexual intercourse was avoided because of anticipation of pain during the previous 4-week period as assessed on the dyspareunia VRS
- Change from baseline to each scheduled assessment in the number of days with uterine bleeding (including spotting) during the previous 4-week period measured by eDiary
- Change from baseline to each scheduled assessment in the number of days when school or work was missed due to EAP in the previous 4-week period as reported in the eDiary
- Change from baseline to each scheduled assessment in the number of days when the subject had to go to bed or lie down due to EAP in the previous 4-week period as reported in the eDiary
- Change from baseline to each scheduled assessment in the Pain, Control and powerlessness, Emotional well-being, Social support, Self-image dimensions and the Modular sexual relationship questionnaire of EHP-30 scores

- Change from baseline to each scheduled assessment in the Health Related Productivity Questionnaire (HRPQ) scores
- Number of non-study endometriosis related health visits, number of days in hospital and type of procedures performed based on Health Resource Utilization Questionnaire (HRUQ) at each scheduled assessment
- Change from baseline to each scheduled assessment in the Physician/Subject Surgery Intention Question (PSIQ/SSIQ)
- Change from baseline to each scheduled assessment in the PROMIS Fatigue – Short Form 6a
- Change from baseline to each scheduled assessment in the EuroQoL 5-Dimension 5-Level (EQ-5D-5L) questionnaire
- Response at each scheduled assessment according to Patient Global Impression of Change (PGIC) (and Post-treatment Patient Global Impression of Change, PPGIC)
- Change from baseline to each scheduled assessment in the monthly PGIS (mPGIS) score

7.2 SAFETY ENDPOINTS

- Change from baseline to each scheduled assessment in BMD measured by DXA of lumbar spine (L1-L4), femoral neck, and total hip
- Incidence and severity of treatment emergent adverse events (TEAEs)
- Incidence and severity of hypoestrogenic TEAEs (hot flush)
- Time to the first post-treatment menses
- Changes in clinical laboratory assessments (hematology, biochemistry, coagulation parameters, hormones, lipids and urinalysis) from baseline to each scheduled assessment
- Any pathological changes from baseline in the endometrium as assessed by histology from endometrial biopsies
- Changes from baseline to each scheduled assessment in any other safety parameter including weight, vital signs, ECG, gynecological assessments and endometrial thickness

7.3 EXPLORATORY ENDPOINTS

- Change from baseline in bone turnover markers at each scheduled assessment
- PK and PD of linzagolix

8 STUDY DESIGN

This is a prospective, randomized, double-blind study.

Subjects who have completed the 6-month Treatment Period in 18-OBE2109-003 - Edelweiss 3 study (herein referred to as main study) will be invited to enter the present extension study. Month 6 visit of

the main study is a decision point for Subjects to either end treatment and enter a post-treatment follow up (part of the main study), or to opt for a 6-month treatment extension.

The extension study starts at the Month 6 visit of the main study. Subjects will be required to sign a specific informed consent form (ICF) for this extension study. Only subjects who have completed the full 6-month Treatment Period in the main study and meet the inclusion criteria will be eligible for entry in the extension study.

All subjects will receive once daily either linzagolix 75 mg alone (with ABT placebo) or 200 mg combined with ABT for 6 months. Subjects who received placebo during the main study will be randomized to either linzagolix 75 mg alone (with ABT placebo) or linzagolix 200 mg with ABT. Subjects who received active treatment during the main study will continue with the same treatment.

After end of treatment in the extension study (6-month treatment period: from Month 6 to Month 12), subjects will enter a post-treatment Follow-Up Period of 6 months with no investigational medicinal product (IMP).

The total duration of the present extension study will be 12 months.

A schematic of the study design is shown in Figure 1.

[figure not shown]

Figure 1 : Study design

All subjects will receive once daily either linzagolix 75 mg alone (with ABT placebo) or linzagolix 200 mg combined with low dose ABT for 6 months. ABT is a combination of estradiol (E2) 1 mg and norethisterone acetate (NETA) 0.5 mg.

Since linzagolix 75 mg and 200 mg tablets have a different appearance, a double-dummy design will be used in order to maintain the blinding of the study.

Linzagolix/placebo tablets will be provided in monthly treatment kits, packaged, labelled and administered in the same manner to protect the blinded nature of the trial.

ABT/placebo treatments will be supplied as 3-monthly kits, packaged, labelled and administered in the same manner to protect the blinded nature of the trial.

Each treatment kit will be labelled with a unique kit number. Treatment kit numbers will be provided through IWRS.

9 STUDY POPULATION

9.1 SUBJECTS

9.1.1 Description of the target population

All subjects who have completed the full 6-month Treatment Period in the main study and who meet the inclusion criteria will be offered to enter the extension study.

9.1.2 Number of subjects

It is estimated that up to 288 subjects will enter the extension study, assuming that 80% of the patients randomized in the main study will complete the study (namely 360 subjects) and that up to 80 % thereof will enter the extension study.

9.1.3 Study region/location

The study will be conducted in the Unites States (US) and Europe, at the same investigational sites as in the main study.

9.2 ENTRY CRITERIA

9.2.1 Inclusion Criteria

To be eligible for inclusion into this extension study, the subjects must **fulfil all** of the following criteria:

1. The subject must provide a written informed consent specific to this study prior to starting the extension study treatment.
2. The subject has completed the 6-month treatment in the main study.

3. The subject is willing and able to continue to comply with the requirements of the study protocol for the duration of the extension study.
4. The subject agrees to continue to use only the analgesic rescue medication permitted by the protocol during the Treatment and Follow-up Periods.
5. If of childbearing potential, the subject agrees to continue to use one of the following birth control methods during the entire Treatment Period of the study and until 3 months after the end of treatment:
 - a. Sexual abstinence, if this is the subject's habitual practice and/or the subject is routinely abstinent from heterosexual intercourse,
 - b. Partner with a vasectomy with confirmed azoospermia,
 - c. Double non-hormonal barrier contraception such as condom or diaphragm each combined with spermicide.

9.2.2 Exclusion Criteria

To be eligible for inclusion in this extension study the subject must **not** meet any of the following criteria:

1. The subject is pregnant or is planning a pregnancy within the duration of the study (including the Follow-up Period).
2. The subject is likely to require treatment during the study with any of the medications listed below:
 - a. GnRH antagonists
 - b. GnRH agonist injections/3-month depot injections
 - c. Danazol
 - d. Oral contraceptives and other sex hormones
 - e. Depot contraceptives
 - f. Selective Progesterone Receptor Modulators (SPRMs), Selective Estrogen Receptor Modulators (SERMs) and aromatase inhibitors
 - g. Long acting narcotics (i.e. requiring less than once daily dosing)
 - h. Systemic glucocorticoid treatments for acute diseases (not depot)
 - i. In situ copper intra-uterine device (IUD)
 - j. In situ IUD with progestogen
3. The subject is likely to use cannabinoids during the study.
4. The subject has any other clinically significant gynecologic condition identified during the main study on transvaginal ultrasound (TVUS), on endometrial biopsy or at the manual breast examination, which might interfere with the study efficacy and safety objectives.
5. The subject has met any of the main study discontinuation criteria including:

- a. Serum calcium level confirmed on a repeated test above 2.9 mmol/L
 - b. BMD decrease from baseline > 8% or a Z-score \leq -2.5 at either femoral neck, hip or spine on the Month 6 DXA scan during the main study.
 - c. QTcF > 500 ms or increase > 60 ms from the highest value prior to first dose during the main study.
 - d. Any of the following elevation of hepatic enzymes:
 - ALT or AST >8xULN
 - ALT or AST >5xULN for more than 2 weeks
 - ALT or AST >3xULN and (TBL >2xULN or INR >1.5)
 - ALT or AST >3xULN with the appearance of fatigue, nausea, vomiting, right upper quadrant pain or tenderness, fever, rash, and/or eosinophilia (>5%)
6. The subject has any condition that, in the opinion of the Investigator, constitutes a risk or a contraindication to the participation of the subject in this extension study or that could interfere with the study objectives, conduct or assessments.

10 STUDY PROCEDURES AND ASSESSMENTS

10.1 GENERAL INSTRUCTIONS

The extension study starts at the Month 6 visit of 18-OBE2109-003 - Edelweiss 3 study (herein referred to as the main study). At Month 5 visit of the main study, the subject will have been informed of the possibility to enter the extension study at Month 6 (if eligible) and will have been provided with a copy of the subject information sheet, specific to the extension study, to read prior to the Month 6 visit.

After all Month 6 assessments have been made, if the subject is eligible, one original copy of the extension-specific ICF will be signed and personally dated by both the subject and the Investigator or legally acceptable designee. The original signed copy will be kept in the confidential investigator file and a copy will be given to the subject. Once the ICF is signed, the subject will be dispensed new treatment kits. She will take her daily dose of study medication at the study site from these newly dispensed kits.

During the whole study, the subject will be identified using a Subject Identification Number (SIN) for all documentation and discussion. The subjects will be identified with the same SIN than in the main study. SINS will be made of 6 digits, as follows:

- 1st, 2nd and 3rd digits: site identifier (100 to 999)
- 4th, 5th and 6th digits: subject number (001 to 999)

An electronic Case Report Form (eCRF) will be completed for all subjects who signed the ICF.

Subjects who previously received placebo in the main study will be randomized in a 1:1 ratio to either linzagolix 75 mg alone (with ABT placebo) or linzagolix 200 mg with ABT.

Subjects who received active treatment in the main study will continue with the same treatment (linzagolix 75 mg alone with ABT placebo or linzagolix 200 mg with ABT).

In order to maintain the blind, the site will not be required to perform any randomization activities. The kits will be automatically allocated to the corresponding patients in the IWRS upon confirmation of their eligibility.

[figure not shown]
Treatment kits will be dispensed to the subjects as follows:

- on Month 6 and Month 9 visits, subject will receive two kits, one for linzagolix/placebo (monthly kit) and one for the ABT/ABT placebo (3-monthly kit).
- On Month 7, Month 8, Month 10 and Month 11 visits, subject will receive one kit only, for linzagolix/placebo.

The treatment kit numbers for linzagolix/placebo and for ABT will refer to unique kits present at site and corresponding to the randomization allocation.

10.2 OUTLINE OF STUDY PROCEDURES AND ASSESSMENTS

The first visit for this extension study is combined with the Month 6 visit of the main study. Therefore, the Month 6 assessments from the main study will not have to be duplicated at the start of the extension study. The study visit schedule is depicted in Figure 2 and the schedule of assessments is detailed in Appendix A and Appendix B.

* At the end of the 6-month follow-up, subjects with a BMD decrease from baseline of > 1.5% for lumbar spine and/or > 2.5% for total hip compared to main study baseline will have an additional DXA scan 6 months later.

Figure 2 : Schedule of Visits

All visits should take place at the end of the defined period (i.e. Month 7 visit should be scheduled at the end of Month 7, Month 8 visit should be scheduled at the end of Month 8, etc.). One month is defined as 28 days/4 weeks. All visit dates are calculated from the date the patient started treatment in the main study (Day 1 visit of 18-OBE2109-003 Edelweiss 3):

- Month 7 (Day 197), Month 8 (Day 225), Month 9 (Day 253), Month 10 (Day 281), Month 11 (Day 309) and Month 12 (Day 337) for the Treatment Period,
- Month 1 Extension FU (Day 365), Month 3 Extension FU (Day 421) and Month 6 Extension FU (Day 505) for the Follow-up Period.

A window of -3/+2 days is allowed for Month 7 visit, and of ± 3 days for each of the following visits during the Treatment Period. A window of ± 7 days/1 week is allowed for each visit scheduled during the Follow-Up Period.

The timing of events is shown in the Schedule of Assessments (Appendix A and Appendix B).

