10.2.1 Treatment Period

During the entire Treatment Period:

- the subject will use the same eDiary as during the main study. The eDiary should be completed daily, in the evening at approximately the same time, for use of provided/prescribed analgesics, uterine bleeding, pelvic pain, dyspareunia, dyschezia and daily function.
- the subject will take her daily dose of study medication at home except on the day of study visits where she will take her daily dose at site. There will be no IMP intake at the Month 12 visit. The last dose of study medication in this extension study will be the dose taken the day before Month 12 visit.
- the subject will be asked to bring her eDiary and her IMP kits at each visit to the site.
- the subject will receive contraception counselling at each visit.
- the subject will be provided/prescribed a limited quantity (as per Investigator's judgement) of standard doses of permitted analgesics as rescue medication for EAP for the duration of the study.
- the subject will receive calcium 500 to 1000 mg and vitamin D 400 IU supplementation which she will be advised to take daily (at least 4 hours from the intake of the study drug) until the end of the study. Intake should be recorded at each study visit in eCRF.
- AEs and concomitant medications will be recorded in the eCRF (excluding any provided/prescribed analgesics used for EAP will be recorded daily in the eDiary only).

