10.2.1.1 Study visit: Month 6 (Day 169 \pm 3 days)

After all Month 6 assessments pertaining to the main study have been made and the subject has been confirmed to be eligible to proceed in the extension study (see section 9.2), the subject will be requested to sign the extension-specific ICF that she was given at the Month 5 visit.

Note: inclusion in the extension study will not be postponed if the results of any Month 6 assessment are not available on the day of Month 6 visit. Subjects will be required to stop the treatment if the results obtained after enrollment meet the discontinuation criteria defined in Section 10.7.2.1.

After signature of the extension-specific ICF, the subject will be dispensed new treatment kits. The subject will take her daily dose of study medication at the study site from these newly dispensed kits. The exact time of dosing (hour/minute) will be recorded in eCRF.

In addition, the subject will:

- receive contraception counselling and will be given double barrier contraception (condoms with spermicide), if requested, to be used until 3 months after treatment end. If the subject is at risk for

acquiring HIV, she must be reminded to use double non-hormonal barrier contraception without spermicides (eg: condoms and diaphragms).

- be provided/prescribed a limited quantity (as per Investigator's judgement) of standard doses of permitted analgesics as rescue medication for EAP for the duration of the study.
- receive calcium 500 to 1000 mg and vitamin D 400 IU supplementation

Upon completion of the visit, the subject will be provided with emergency contact phone numbers and will be scheduled for her next visits.

10.2.1.2 Study visits: Month 7 (Day 197 -3/+2 days) and Month 8 (Day 225 ± 3 days)

The following tests and evaluations will be performed :

- eDiary completion compliance check
- ePRO and ClinRO completion, ideally before any other procedures or assessments:
 - at Month 7 visit: EHP-30, EQ-5D-5L, PROMIS, mPGIS, PGIC, HRUQ, HRPQ with mPGIS and PGIC completed last
 - at Month 8 visit: mPGIS, PGIC, HRUQ and HRPQ with mPGIS and PGIC completed last.
- Concomitant treatments recording
- AE recording
- Completion of the paper C-SSRS questionnaire (version for "already enrolled subjects" (see Appendix S) for patients responding to the C-SSRS for the first time during the study, or version "since last study visit" (see Appendix T) for patients for whom the C-SSRS was completed at the previous study visit)

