11.2 DOSAGE AND ADMINISTRATION

Linzagolix treatments and matching placebo will be supplied as film-coated tablets for oral administration and given as monthly treatment kits (Figure 5).

ABT and corresponding placebo will be supplied as red capsules and given as 3-monthly treatment kits.

IMP treatment will be administered once daily up to Month 12 inclusive. The subjects will have to swallow one tablet of linzagolix, one tablet of linzagolix placebo and one capsule of ABT or ABT placebo, ideally at the same time each day.

On the day of a study visit, the subject must take the study medication at site. The site staff will record in the eCRF the time of study medication intake. The linzagolix/placebo tablets must be taken from the kits dispensed on that visit (and not from the previously dispensed kits). On Month 6 and Month 9 visits, ABT/placebo capsules must be taken from the kits dispensed during these visits. On Month 7, 8, 10 and 11 visits, ABT/placebo capsules must be taken from the previously dispensed kits.

The treatment groups are described below:

Treatment group	Daily dose Month 6 to Month 12			
	Linzagolix active tablets	Linzagolix placebo tablets	ABT active capsules	ABT placebo capsules
75 mg	1 × 75 mg	1 × placebo 200 mg	None	1 capsule
200 mg + ABT	1 × 200 mg	1 × placebo 75 mg	1 capsule	None

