11.3 PACKAGING AND LABELLING

Linzagolix/placebo will be provided by the Sponsor (or delegate) as monthly kits.

On Month 6, 7, 8, 9, 10 and 11 visits, the subject will be given a wallet card containing four blisters in total:

- Two blisters of 15 tablets each of 200 mg linzagolix or matching placebo (corresponding to the grey card on Figure 5),
- Two blisters of 15 tablets each of 75 mg linzagolix or matching placebo (corresponding to the pink card on Figure 5).

This kit covers 30 days of treatment.

[figure not shown]

Figure 5 : Linzagolix kit design

Each linzagolix/placebo kit will be labeled with a unique kit number from K50001 to K60000 (6-characters). The blisters being attached into the wallet card, linzagolix/placebo kit is considered as a single unit and therefore labelling on the wallet is sufficient (individual blisters are not labelled).

ABT and matching placebo will be provided by the Sponsor (or delegate) as 3-monthly kits.

On Month 6 and 9 visits, the subject will be given a carton box containing 14 blisters of seven capsules each of ABT or matching placebo. This kit covers 98 days of treatment.

Each ABT kit will be labeled with a unique kit number (different from the linzagolix kit number), from A50001 to A70001.

Each kit of linzagolix/placebo or ABT/placebo will have a label including a tear-off part. The tear-off part containing the study number and the kit number will be placed into a drug accountability form at site.

Labels will be printed in the local language of the countries where the study will take place in accordance with applicable local regulations, the recommendations of GMP guideline (Annex 13) and FDA 21 CFR 312.6 part.

The kit label, i.e. on the secondary packaging, will indicate at least the following items:

- Protocol number
- Kit number
- Batch number
- Expiry date (for Europe only)
- Storage conditions
- Sponsor name and address

Label examples are filed in the study file at the Investigator's site and in the trial master file.

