Appendix A. Schedule of study assessments – Treatment Period

Schedule of study assessments – Treatment Period							
Timing ¹	Treatment Period						
	M6 ²	M7	M8	M9	M10	M11	M12
Informed Consent	X						
Inclusion-Exclusion criteria	X						
Physical examination (including weight)	X			X			X
Columbia-Suicide Severity Rating Scale	X	X	X	X	X	X	X
ECG ³	X	X	X	X	X	X	X
Vital signs	X	X	X	X	X	X	X
Urine pregnancy test	X	X	X	X	X	X	X
Endometrium TVUS	X			X			X
Gynecological examination	X			X			X
Endometrial biopsy	X ⁴						X ⁴
Manual breast examination	X						X
Clinical laboratory & urinary protein dipstick	X ⁵	X	X	X ⁵	X	X	X ⁵
BMD by DXA	X			X ⁶			X
Adverse events	X	X	X	X	X	X	X
Concomitant medication	X	X	X	X	X	X	X
Contraceptive dispensing and counselling	X	X	X	X	X	X	X
Permitted analgesic prescribing/dispensing	X	X	X	X	X	X	X
Vitamin D and calcium dispensing	X	X	X	X	X	X	X
Subject eDiary completion check	X	X	X	X	X	X	X

¹ All visits should take place at the end of the defined period (i.e. M7 visit should be scheduled at the end of Month 7, M8 visit should be scheduled at the end of Month 8, etc.). All visit dates should be calculated from the date of Day 1 visit (in the main study). A month is defined as 28 days/4 weeks. Visits should be scheduled ± 3 days (-3/+ 2 days for Month 7 visit) from the calculated date.

² All Month 6 assessments except informed consent and inclusion/exclusion criteria would have been performed as part of the main study (18-OBE2109-003 - Edelweiss 3).

³ ECG should be performed at about the same time but before the PK sample

⁴ If endometrium thickness in TVUS is ≤ 5 mm, no endometrial biopsy will be necessary.

⁵ Overnight fasting is required.

⁶ Only for subjects who met the following criterion at any site on the M6 DXA scan: $-2.5 < Z\text{-score} \leq -1.5$

Schedule of study assessments – Treatment Period (cont'd)

Schedule of study assessments – Treatment Period							
Timing ¹	Treatment Period						
	M6 ²	M7	M8	M9	M10	M11	M12
IMP accountability	X	X	X	X	X	X	X
Dispense linzagolix/placebo kit	X	X	X	X	X	X	
Dispense ABT/placebo kit	X			X			
EHP-30, EQ-5D-5L and PROMIS ³	X	X		X			X
mPGIS, PGIC, HRUQ and HRPQ ³	X	X	X	X	X	X	X
SSIQ and PSIQ ³	X						X
Blood sample for PK ⁴	X	X	X	X	X	X	X
E2, LH, P4	X	X	X	X	X	X	X
SHBG	X			X			X
Bone biomarkers	X			X			X

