¹ All visits should take place at the end of the defined period (i.e. M7 visit should be scheduled at the end of Month 7, M8 visit should be scheduled at the end of Month 8, etc.). All visit dates should be calculated from the date of Day 1 visit (in the main study). A month is defined as 28 days/4 weeks. Visits should be scheduled \pm 3 days from the calculated date.

² All Month 6 assessments except informed consent and inclusion/exclusion criteria would have been performed as part of the main study.

³ ClinROs (PSIQ and HRUQ) will be administered to the subject by the site staff and the responses will be filled in the eDiary. ePROs (EHP-30, EQ-5D-5L, PROMIS, PGIS, PGIC, HRPQ and SSIQ) will be filled in by the subject in the eDiary.

⁴ PK samples should be taken after the ECG and before the daily dose of IMP.

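### The 30-day linzagolix kit can run out before Month 7 or Month 8 when the Month 6 visit is early, so a compliant woman can miss up to 3 days of tablets

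*Protocol*

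**What the plan says.** **Supply.** Protocol 11.3 describes the linzagolix/placebo wallet as two blisters of 15 tablets per strength: "This kit covers 30 days of treatment". Section 10.1 dispenses one such wallet at Month 6 and Month 9 (with an ABT kit) and adds: "On Month 7, Month 8, Month 10 and Month 11 visits, subject will receive one kit only, for linzagolix/placebo". The ABT kit holds 14 × 7 = 98 capsules.

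**Visit dates.** Section 10.2 counts every visit from main-study Day 1. The heading of 10.2.1.1 gives "Study visit: Month 6 (Day 169", plus or minus 3 days. For the next visit, 10.2 says "A window of -3/+2 days is allowed for Month 7 visit" (nominal Day 197). Months 8 to 12 are plus or minus 3 days around Days 225, 253, 281, 309 and 337.

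**Which kit supplies which dose.** Section 11.2: "On the day of a study visit, the subject must take the study medication at site". That dose must come from the kit dispensed at the visit. Section 10.2.1.1 applies the same rule at Month 6. There is no dose at the Month 12 visit. Women bring their packs back (10.2.1: "the subject will be asked to bring her eDiary and her IMP kits at each visit to the site"), but no section says whether leftover tablets from an earlier kit may be used at home.

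**Appendix A.** Footnote 1 on the first page carries the Month 7 exception (minus "3/+ 2 days for Month 7 visit) from the calculated date"). The same footnote on the continuation page gives only plus or minus "3 days from the calculated date" for all visits. SAP 9.6 repeats both versions.

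**The concern.** The tighter +2 limit at Month 7 looks meant to keep the first extension interval within one 30-day kit. It is tied to main-study Day 1, however, while the kit starts on the actual Month 6 day, which may be up to 3 days early. No earlier extension kit can fill the gap, and no section provides a spare kit or ties Month 7 to the dispensing date.

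What is at stake is narrow:

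- Month 7 and Month 8 are sampling visits for pre-dose PK and for E2, LH and P4. After three missed days the last dose is about 96 hours before the sample, not 24. At the half-life of 15 to 20 hours in Protocol 5.5.1, the extra 72 hours is 4.8 to 3.6 half-lives. That leaves roughly 4% to 8% of the usual trough.
- SAP 5.5 would keep such a PK sample. It requires pre-dose sampling within 10 days of the theoretical visit, and its limit of 2 days after last intake is written for Month 12 only. SAP 6.6.3 tabulates E2 categories at each visit.
- The ABT kit does not run out, so a woman on 200 mg with ABT could take ABT alone on the missing days.

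**Working it through.** **Inputs.** Tablets per kit and strength: 2 × 15 = 30, one per day, which reproduces the 30 days in 11.3. Windows (10.2, 10.2.1.1): Month 6 Day 166–172, Month 7 Day 194–199, Month 8 Day 222–228, then nominal ± 3. Main-study tablets are not counted (assumption).

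**Formula.** The visit-day dose comes from the new kit, so doses needed = next visit day − dispensing day. Shortfall = max(0, doses needed − tablets in hand).

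**Worst case by Month 6 day, leftovers used**

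| Month 6 | Doses to Day 199 | Short of 30 | Doses to Day 228 | Short of 60 |
|---|---|---|---|---|
| Day 166 | 33 | 3 | 62 | 2 |
| Day 167 | 32 | 2 | 61 | 1 |
| Day 168 | 31 | 1 | 60 | 0 |
| Day 169 | 30 | 0 | 59 | 0 |

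By Month 9 the longest span is 256 − 166 = 90 days against 90 tablets, so nothing is short from there on. The longest ABT interval is also 90 days (256 − 166, or 340 − 250), under 98.

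**How many schedules.** There are 7 × 6 × 7⁵ = 705,894 in-window schedules from Month 6 to Month 12.

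- Before Month 7: 6 of the 42 Month 6/Month 7 pairs fall short, 14.3%.
- Before Month 8: 3.7%.
- Either: 124,852 of 705,894 = 17.7%. About 9.2% lose one day, 6.1% two and 2.4% three. The mean over all schedules is 0.29 days.
- By Month 6 day: 64% at Day 166, 43% at Day 167, 17% at Day 168, none from Day 169.

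These percentages treat visit days as independent and uniform. With 50% or 70% of visits on the nominal day and the rest spread evenly, 9% or 5% fall short (mean 0.13 or 0.07 days).

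**If leftovers may not be used.** Later intervals can reach 34 days (for example Day 194 to 228), 4 days short of one kit, even after an on-time Month 6. The mean total over six intervals is 2.35 days if uniform, or 1.19 or 0.65 if clustered.

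**If a site follows the continuation footnote.** Month 7 may be Day 200. An on-time Day 169 then needs 31 doses. With leftovers used, the maximum is 4 days and 23% of uniform schedules fall short.

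**The case against.** The arithmetic is not in dispute; its weight is.

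- **Three days is the corner case.** It needs Day 166 followed by Day 199, one pair in 42. About half of the short schedules lose a single day. The Month 8 span never raises the total above 3.
- **The percentages are not data.** The documents give no visit-day distribution, and the site books the next visits at the end of Month 6, knowing the dispensing date. From Day 166, Days 194 to 196 are in window and fully covered.
- **No section forbids leftovers.** Section 11.2 bars earlier kits only for the visit-day dose. The no-carry-over figures rest on a rule the protocol does not state.
- **Three statements give −3/+2** (10.2, the heading of 10.2.1.2 and the first Appendix A page). One footnote omits it.
- **The effect is small.** The study is descriptive, PK is exploratory, dose times on the four previous days are recorded, and 3 days of 168 is 1.8% of dosing.

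Most of this stands, and it limits the point's importance. It does not remove it. Nothing tells sites to book earlier after an early Month 6 visit, and even the nominal Day 197 is 31 days after Day 166. The percentages should be read as illustrations, and the no-carry-over and footnote cases as conditional.

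**Conclusion.** The concern holds, as a minor one. The windows and kit size together allow a woman who follows the protocol to be without linzagolix tablets for 1 to 3 days before Month 7, or 1 to 2 days before Month 8, whenever Month 6 falls on Day 166 to 168 and the next visits are late enough. This follows from the stated windows and tablet counts, given that no main-study tablets are used. How often it happens is unknown: 5% to 18% of schedules under the assumed visit-day patterns.

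With leftovers used, nothing after Month 8 is touched. The Month 12 primary window, which ends at the last treatment date (SAP 5.2.1), is then unaffected. The exposed data are some Month 7 and Month 8 PK and hormone samples. The two Appendix A footnotes conflict and need correcting in any case.

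**What to change.** 1. In 11.2 or 11.3, state that leftover linzagolix/placebo tablets from earlier extension kits are kept and used at home before the next visit.
2. In 10.2 and both versions of Appendix A footnote 1, require Month 7 no later than 30 days and Month 8 no later than 60 days after the Month 6 dispensing date. Alternatively, dispense enough tablets for the longest allowed interval.
3. Put the Month 7 exception in the continuation footnote, and carry the correction into SAP 9.6.

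The first change alone does not close the gap, because the first interval has no leftovers to draw on. With the first two together, 581,042 in-window schedules remain and none runs short. The 705,894 − 581,042 = 124,852 removed are exactly those that ran short.

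The cost is one dispensing sentence and one window sentence, with no new visit or assessment. The downside is a second anchor date and a tighter window after an early Month 6: from Day 166, Month 7 by Day 196 and Month 8 by Day 226. Some visits now in window would become deviations.
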